8.8 QUALITY CONTOL

8.8.1 Study Documentation

Validation of questionnaire

The questionnaire will be tested by targeted HCPs (at least one per speciality) in each country for their comprehensibility, consistency, and the appropriateness of medical terms used. The questionnaires will be translated from English into local language using the back and forth method to ensure an accurate translation of the local versions of the questionnaire. Translation and back translation will be performed by personnel.

Approaches for validating the results

The quality control for validating the results will be conducted at five levels:

 At data collection level, the survey data will be collected using a secure online electronic data capture (EDC) survey system. The proposed data entry system has been tested and is secure for receiving and storing survey data. A webbased data repository will be used to warehouse survey data and other relevant program information. This EDC system is an EU Annex 11 and 21 Code of Federal Regulations Part 11 compliant platform for the entry, storage, manipulation, analysis, and transmission of electronic information. This platform ensures compliance with all relevant regulatory guidelines and is already used in several PRAC-approved surveys (European Network of Centres for Pharmacoepidemiology and Pharmacovigilance study register).¹ All data entered will be single data entry directly done by the respondent or the interviewer in the case of phone interviews. Verification of the reliability and security of the web questionnaire interface will be done by **and the case of the qualified data manager will perform the monitoring of the quality and datasets definition**.

- 2. At the study database level, final data quality checks will be applied (beyond data management process):
 - Identification and count of non-analysable questionnaires: estimation of the percentage of HCPs without complete analysable questionnaire
 - Any changes in the database will be tracked and documented. The countrydatasets will be stored in a dedicated database. Once data is validated and quality checked, the database will be locked
- 3. At the statistical analysis level: all data management and statistical analyses programs developed and used in the analyses will be documented. All versions generated will be dated, kept with accompanying documentation and archived. The original database will be stored. A derived database will be created for the new versions of the data in order to include recoding and computing of new variables, especially stratification of continuous variables, combination of modalities for categorical variables, calculation of composite indicators, etc.
- 4. At the results level, a data review will be done to ensure data integrity.
- 5. At the study level, all aspects of the study will be conducted according to the SOPs of and and divisions. According to the SOPs, an independent review of the survey results and report will be conducted by a person who was not in charge of their preparation.

8.8.2 Site Audits and Inspections

Not applicable.

8.8.3 Safeguards, security and traceability of contacts

Operators of the call centre specialised in health surveys, will be assigned to the project and trained on the survey methodology prior to fieldwork. The email contacts will be traced using the management software.

8.8.4 Retention of Records

The study documentation will be stored in the study master file.

The data from the web questionnaires and the phone interviews will be stored on the survey database for 5 years.

¹ European Network of Centres for Pharmacoepidemiology and Pharmacovigilance (ENCePP). http://www.encepp.eu/encepp/studySearch.htm: EUPAS11379, EUPAS11765, EUPAS6355, EUPAS9871

Data storage will be in line with national data protection requirements for each of the countries where the study will be conducted.

All documentation pertaining to the study, including paper and electronic records will be retained for a minimum of 5 years after the end of the study, in accordance with Standards.

8.9 LIMITATIONS OF THE RESEARCH METHOD

Bias

The potential for selection bias of HCPs participating in a survey is an inherent bias/limitation to any study based on volunteer participation.

Among non-response bias, targeted HCPs may also have activated filters in their mail box to block spams and unsolicited emails. They may not even see the invitation to participate in the survey if a very strict degree of message filtering is set. Having multiple email addresses could also be a critical situation. If the one used is not the primary address or if the HCPs do not check their email box frequently they will not receive the invitation during the recruitment period. This is one of the reasons why the HCPs will also be contacted by phone.

Moreover, web surveys may promote social desirability bias which refers to the tendency of physicians to give socially desirable/expected responses instead of choosing those reflecting their current knowledge or clinical practice, e.g., physicians can copy-paste information gathered online instead of giving their own opinions (Wyatt 2000). Social desirability can affect the validity of survey research findings, but the use of prepopulated items in the questionnaire could/tends to reduce this bias (Nederhof 1985).

The access to the web questionnaire interface will be strictly limited to the invited participants, with the possibility to participate only once and a traceability system. Thus, stakeholder bias (multiple answers of people who have a personal interest in survey results and/or who incite peers to fulfil the survey to influence the results) or unverified respondents (when it is not possible to verify who responds) are not applicable.

Limits inherent to surveys

In such surveys, the generalisation and external validity of the results is restricted to HCPs who have an active email address or phone number and are willing (and able) to answer a questionnaire. These HCPs may not be fully representative of the whole targeted HCP population (Wyatt 2000).

Generalisation of the survey results

The raw survey results cannot be generalized to the overall HCP target population, except if a sample adjustment is applied. For more transparency and accuracy, both unweighted (i.e., raw data) and weighted results will be presented in the report.

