- HCPs can also choose to participate in the survey by phone in the local language. In this case, an appointment for a phone interview will be scheduled with them

- HCPs who self-report having treated patients with Alecensa at least once in the 6 months prior to the study and are not employed by a pharmaceutical company,
 , or by regulatory bodies will be eligible to complete the survey. Both parameters are included as screening questions in the questionnaire
- Once HCPs have passed the screening questions of the questionnaire, they are moved through the questions one question at a time. HCPs can only progress to the next question when the previous question was answered. Only wholly completed questionnaires can be submitted
- If the questionnaire is not completed within one week, the HCPs will be sent a reminder by email one week after the link was sent to them
- If the study sample size is not achieved in the stratum (speciality/country), a second reminder by phone will be conducted 1.5 weeks after the link has been sent
- If the questionnaire is still not fully completed, a third and final reminder will be sent to the HCPs by email approximately three weeks after the start of the survey

If necessary, i.e., if the minimum number of needed responders is still not reached, the recruitment will be continued to achieve the study sample size-in a specific stratum.

A HCP will be considered as unreachable if he/she has been contacted between 3 and 5 times without any answer being received.

For each HCP of the sample, the number of contacts, and the date and time when he/she completed the web questionnaire will be recorded. The recruitments in each stratum (HCP speciality/country) will be stopped when the target is reached. If the files have been exhausted in any particular stratum, the recruitments in this stratum will be prematurely ended and a strategy will be determined to adjust the sample size with associated weighting.

The number of HCPs passing the screening questions, incidence rate, and the survey response rate will be monitored regularly by **series**. If the survey response rate or incidence rate is too low, the recruitment may be undertaken in additional countries.

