8.5.3 Sample adjustment

Since the relative weight of each country and each category of HCPs in the final sample may be different from its real proportion, the extrapolation of the raw survey results to the overall target population would not be relevant without adjustment. The survey results will be weighted to reflect the real proportion of the countries and the real proportion of each speciality in order to allow the extension of the survey results to the

Alecensa—F. Hoffmann-La Roche Ltd Protocol BO40643, Version 1 overall target population. Both unweighted and weighted results will be presented in the report.

A weight variable will be applied to each statistical unit (i.e., the HCPs) during the results calculation to correct any over-or under-sampling that may have occurred for a country or speciality. This weight variable will indicate how many unit(s) of the population of interest an observation will count in a statistical procedure. Its value will change per country and per speciality. The weights will be normalized to obtain their sum equal to the sample size.

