Knowledge questions (Questions Q5 to Q8 of HCP questionnaire): For each question, the number and percentage of HCPs answering correctly each subquestion will be presented. Subsequently, individual HCP knowledge scores will be calculated as the percentage of correctly answered knowledge questions; scores will range from 0 to 100% with 100% representing the percentage of all knowledge questions being answered correctly. HCP knowledge level will be calculated as the mean of individual scores.

Clinical practice questions (Questions Q9 and Q10 of HCP questionnaire): For each question, HCPs answering correctly each sub-question will be presented. Subsequently, individual HCP clinical practice scores will be calculated as the percentage of correctly answered survey questions; scores will range from 0 to 100% with 100% representing the percentage of all clinical practice questions being answered correctly. HCP clinical practice level will be calculated as the mean of individual scores.

In a first step, calculations will be performed on raw data. No projection factor will be applied to generalize the results to the entire prescribers' universe. As a consequence, the line "Overall - unweighted results" will show only the results observed on the overall sample and will not reflect the countries' universe since this sample is not proportional to the size of the lists in each country.

In a second step, the results will be weighted according to the real proportion of HCPs in each country in order to accurately reflect the population that the survey seeks to measure.

Possible selection bias will be assessed by comparing the distributions of available characteristics (e.g., country, type of setting (hospital or office-based), and speciality, if applicable and feasible) between respondent and non-respondent HCPs.

Moreover, the profile of HCPs with incorrect answers could be identified and described with all available relevant covariates collected in the survey (e.g., country, duration of practice, type of setting, and speciality) and past experience with Alecensa (number of patients treated).

Assessment of success

A successful outcome on the effectiveness of risk minimisation measures is defined a priori by the following target levels:

- Proportion of HCPs being aware of the important identified risk and related minimisation measures for Alecensa (Question Q2 and Q3 of HCP questionnaire) – Success: ≥75%

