8.10 OTHER ASPECTS

Strengths of the research methods:

- 1. The information contained in the **sector** file of each country is updated constantly with proactive updates. Quality controls are implemented on a regular basis.
- 2. The sampling of HCPs follows a stratified randomized method which guarantees the representativeness of the contacted population to limit selection bias due to voluntary participation. HCPs will be contacted up to five times before moving forward to other HCPs in the lists.

- 3. The questionnaire includes general questions followed by specific ones to limit a learning process during the survey. As the HCPs may understand the right answer in subsequent questions, it would not be possible to go back in the questionnaire and edit answers in former questions.
- 4. The questionnaire is tested for its clarity. It is also checked whether there are questions which would suggest a specific answer for any reason for example social desirability. The translation of the questionnaire is tested before implementation.
- 5. The study is conducted by an experienced team specialised in the design and conduct of such surveys in the area of safety. It follows SOPs as well as the methodological guidelines on European Network of Centres for Pharmacoepidemiology and Pharmacovigilance and EMEA GVP.

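### Country and speciality weights correct the sampling mix, not who volunteers, so they cannot by themselves carry the results to the overall target population as 8.5.3, 8.7 and 8.9 say

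*Protocol*

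**What the plan says.** **Claim of generalisability.** Section 8.9, under generalisation, states: "The raw survey results cannot be generalized to the overall HCP target population, except if a sample adjustment is applied". Section 8.5.3 describes the weighting in these words: "weighted to reflect the real proportion of the countries and the real proportion of each speciality in order to allow the extension". The extension meant there is from the sample to all HCPs targeted. Section 8.7 and the synopsis say that weighting by the real share of HCPs in each country makes the results mirror the population of interest.

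**What the adjustment consists of.** Section 8.5.3 gives its purpose as "to correct any over-or under-sampling that may have occurred for a country or speciality" and says of the weight: "Its value will change per country and per speciality". No other variable enters it.

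**What the same section concedes.** One paragraph before the generalisation statement, 8.9 restricts external validity to HCPs who can be reached and are willing and able to answer, and adds: "These HCPs may not be fully representative of the whole targeted HCP population".

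**Sampling as a strength.** Section 8.10 says the stratified random method "guarantees the representativeness of the contacted population to limit selection bias due to voluntary participation".

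**Planned check.** Section 8.7 will compare characteristics such as country, "type of setting (hospital or office-based), and speciality, if applicable and feasible) between respondent and non-respondent HCPs". The comparison is descriptive. No consequence for the estimate or for the generalisation statement is given.

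**The concern.** Two different problems are treated as one. The first is the disproportionate country split in Table 3, which the plan creates on purpose and which known weights can undo. The second is self-selection among those invited, which weights built from country and speciality cannot undo. Sections 8.5.3, 8.7 and 8.9 offer the cure for the first as sufficient for generalisation, although 8.9 has just described the second.

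At stake is what the weighted awareness, knowledge and practice results may be said to show. They are to be judged against 75%, 60% and 75%. Section 8.7 states these as levels, with no confidence limit attached. A bias larger than the observed margin over a target is therefore enough to reverse the conclusion for that domain, even when it is smaller than the confidence interval.

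**Working it through.** **Inputs from the protocol.** 200 completed questionnaires, about 2,000 invited, 10% response, P = 50%, z = 1.96 and ±6.9 at n = 200 (8.5.1, Table 2); list sizes and country targets (8.5.2, Table 3); targets of 75/60/75% (8.7).

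**Inputs not in the protocol, assumed here.** The share of invitees who are eligible (treated a patient with Alecensa in the last 6 months), and the difference d between respondents and non-respondents in a domain.

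**1. The plan's own figures.** 1.96 × √(0.5 × 0.5 / 200) = 6.93 points, which matches ±6.9. 200 / 0.10 = 2,000 invitations, which also matches.

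**2. What the weights do to within-stratum non-response.** Let stratum h (country by speciality) have population share W_h, taken as correct, response r_h among eligible HCPs, respondent level R_h and non-respondent level N_h.

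- Weighted survey result: Σ W_h R_h
- Population level: Σ W_h [r_h R_h + (1 − r_h) N_h]
- Difference: Σ W_h (1 − r_h)(R_h − N_h)

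Perfect weights fix W_h and leave (1 − r_h)(R_h − N_h) untouched. With equal r and d across strata the bias is (1 − r) × d.

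**3. Response among eligible HCPs.** The planned 10% is completes over all invited, so it mixes eligibility with willingness. r = 200 / (2,000 × eligible share):

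- all eligible: 10%
- half eligible: 20%
- a quarter eligible: 40%
- a tenth eligible: 100%

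**4. Bias in percentage points, (1 − r) × d.**

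| Response r among eligible | d = 5 | d = 10 | d at which bias reaches 6.93 |
|---|---|---|---|
| 10% | 4.5 | 9.0 | 6.93/0.90 = 7.7 |
| 20% | 4.0 | 8.0 | 6.93/0.80 = 8.7 |
| 40% | 3.0 | 6.0 | 6.93/0.60 = 11.6 |
| 100% | 0 | 0 | none |

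Two of the six cells with incomplete response exceed ±6.9 and four do not.

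**5. The yardstick itself.** ±6.9 is for an unweighted result at P = 50%. Weighting the Table 3 country split to its lists (5,300 + 5,200 + 2,300 + 900 + 1,200 + 900 = 15,800) gives a Kish design effect of 1.15. The half-width becomes 6.93 × √1.15 = 7.4, and the break-even d at 10% response becomes 7.4/0.90, about 8.3 points. At a level of 75% the unweighted half-width is 6.0. The comparison moves somewhat in either direction, but the conclusion does not change.

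**6. Tipping point against a target.** With observed level R and target T, the target is missed in the population when N is below (T − rR)/(1 − r). For an illustrative R = 80% and T = 75%:

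- r = 10%: (75 − 8)/0.90 = 74.4%
- r = 20%: (75 − 16)/0.80 = 73.8%
- r = 40%: (75 − 32)/0.60 = 71.7%

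A five-point margin over the target is therefore lost if non-respondents lie about 5.6, 6.3 or 8.3 points below respondents.

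**7. Section 8.10.** Random selection decides who is invited. It has no influence on who accepts, which is what voluntary-participation bias means. The repeat contacts in the same item can raise response and are a different matter.

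**The case against.** **The limitation is disclosed.** Section 8.9 calls volunteer selection an inherent limitation, discusses non-response and restricts external validity. Section 8.5.3 states the purpose of the weights correctly. The 8.9 sentence can be read as making adjustment necessary rather than sufficient. This stands in part: a reader might infer that volunteer bias is concealed, and it is not. But 8.5.3 and 8.7 are not worded as a mere necessary condition. They say the weighting achieves the extension, and that conflicts with the disclosure.

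**Mitigation is planned.** There are reminders by email and phone, up to five contacts, participation rates by country and speciality, and the respondent/non-respondent comparison. All of this stands. None of it changes what the weighted estimate represents.

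**The magnitude is assumed.** This stands. A reader might infer that the weighted results will be too favourable because volunteers know more, or that an observed 80% hides a true 71% (0.1 × 80 + 0.9 × 70). The documents support neither. They give no difference and no direction. The 71% also requires every invitee to be eligible, whereas the protocol describes invitees as potential prescribers, screens them, and sets the number of invitations partly so that enough pass screening. Section 8.5.1 labels ±6.9 as statistical precision and does not say that it covers bias.

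**Table 3 is no evidence of volunteer bias.** A reader might cite its uneven ratios of target to list size (45/5,200 = 0.87% in the United Kingdom, 20/900 = 2.22% in Austria and Sweden). Those are completed questionnaires, not contacts, and country imbalance is exactly what the weights repair.

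**Further adjustment is debatable.** This also stands. Setting is available for non-respondents only where feasible, and three countries have 20 completes each. Section 8.4.2 says: "For each HCP of the sample, the number of contacts, and the date and time when he/she completed the web questionnaire will be recorded". But the phone reminder is sent only when a stratum is short of its target, and recruitment stops once the target is reached. The number of contacts therefore partly reflects quota timing rather than reluctance.

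**Conclusion.** The point holds as a fault in what the protocol says its weighting achieves. Sections 8.5.3, 8.7 and 8.9 attribute to country/speciality weights a generalisability that they cannot supply and that 8.9 itself limits. The 8.10 statement about random sampling and voluntary participation is wrong. Since the protocol fixes both the weighting variables and the inference, this is not detail awaiting a statistical analysis plan.

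The size is conditional. Over the assumed range (d of 5 or 10 points; 10%, 20% or 40% response among eligible HCPs) the bias is 3 to 9 points, and it is zero if every eligible invitee responds. It can exceed ±6.9 but need not. It should be corrected because the conclusions are read against fixed targets, where a few points may decide. It does not make the survey uninterpretable, and it does not show that the targets would be falsely met.

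**What to change.** 1. **Synopsis, 8.5.3, 8.7 and 8.9:** state that weighting corrects only the country and speciality mix, that weighted results remain subject to non-response bias, and that ±6.9 covers sampling error only.
2. **8.10:** remove the statement that stratified random sampling limits voluntary-participation bias. The sentence on repeat contacts can stay.
3. **8.7:** add a tipping-point table. For each of the three targets, and over a range of assumed response rates among eligible HCPs, it gives the non-respondent level below which the target would be missed, from (T − rR)/(1 − r). The range has to be assumed because the 8.7 response rate counts only completers, partial responders and explicit refusals, so it leaves out invitees who never answer.

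Raking on setting and tables by number of contacts are not requested, for the reasons given above.

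**Cost:** wording changes, one extra table from results already planned, and a less favourable statement of generalisability. No new data are needed and the sample size does not change.

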8.10 OTHER ASPECTS

Strengths of the research methods:

- 1. The information contained in the **sector** file of each country is updated constantly with proactive updates. Quality controls are implemented on a regular basis.
- 2. The sampling of HCPs follows a stratified randomized method which guarantees the representativeness of the contacted population to limit selection bias due to voluntary participation. HCPs will be contacted up to five times before moving forward to other HCPs in the lists.

- 3. The questionnaire includes general questions followed by specific ones to limit a learning process during the survey. As the HCPs may understand the right answer in subsequent questions, it would not be possible to go back in the questionnaire and edit answers in former questions.
- 4. The questionnaire is tested for its clarity. It is also checked whether there are questions which would suggest a specific answer for any reason for example social desirability. The translation of the questionnaire is tested before implementation.
- 5. The study is conducted by an experienced team specialised in the design and conduct of such surveys in the area of safety. It follows SOPs as well as the methodological guidelines on European Network of Centres for Pharmacoepidemiology and Pharmacovigilance and EMEA GVP.

